
small heartrate monitor device, the FirstBeat Bodyguard 2 on their child's chest the night before (and then again on the morning of each of the Laboratory School visits. The devices are small, unobtrusive and do not require an uncomfortable halter band as they easily affix with two small hypoallergenic adhesive electrodes designed to remain comfortable and has been found to remain in place during moderate to heavy physical activity, safe and acceptable in children ages 7-9. Additionally, this device has been found safe and feasibly deployed in studies in both typically developing children and specials population as young as 4 years of age. FirstBeat devices will be distributed to parents at the same time as the saliva kits and parents will receive verbal and written instructions on how and when to affix and remove the device. At the conclusion of each Laboratory School visit, parents will remove the device from their child prior to departure. De-identified heartrate data collected on the device will be immediately downloaded to [name] protected drive in Health Sciences for analysis.

Provide precise definitions of the study endpoints and criteria for evaluation; if the primary outcomes are derived from several measurements (i.e., composite variables) or if endpoints are based composite variables, then describe precisely how the composite variables are derived:

See above

Statistical Considerations

Is a statistical analysis plan appropriate for this qualitative study design?

Yes

Describe the statistical methods for the stated specific aims and hypotheses. Your analysis plans should match the stated study specific aims and hypotheses:

Statistical Method per Outcome Specific Aim 1: Replicate Previous Favorable Behavioral Response to AAI Primary Main Outcome: Behavior responses. This parallel-group randomized design and will utilize a multi-method and multi-source assessment protocol. The assessment protocol will use a repeated-measure within-subject design, gathering main outcomes at three time points to assess the efficacy of AAI on outcomes for children with ADHD who are participating in a short-term intervention with or without the assistance of certified therapy dogs (see Figure 1). Our previous research indicated that after just 2 weeks of intervention, participants in the AAI condition showed significantly greater improvement in symptoms compared to control participants and that these gains were maximized by 10 weeks and then maintained at 6 weeks post intervention ([name] et al., 2018a), suggesting that 10 weeks is an ideal duration of treatment to detect significant benefits from AAI with dogs. Outcomes from AAI utilizing a manualized treatment with therapy dogs (AAI) will be compared to standard of care evidence-based psychosocial treatment at usual (control). Specific Aim 2: Determine Physiological Response over time to AAI for children with ADHD. Exploratory Main Outcome: Diurnal HPA and ANS responses. To determine if children with ADHD present with measurable changes in physiological responses to a short-term AAI (10 weeks) on measures of HPA and ANS we will gather candidate salivary analytes (salivary cortisol, uric acid, and alpha-amylase; Cort, sUA, sAA, respectively) and measures of cardiac rhythm, (heart rate variability; HRV) prior to and post intervention for children participating in both treatment conditions before, immediately after, and upon treatment follow up. Specifically, for each domain we will ascertain changes in diurnal patterns of candidate physiological measures utilizing a linear, repeated measures design gathered across three (3) points in time; establishing individual baseline patterns, end of treatment patterns, and then patterns at 6 weeks post-treatment. Specific Aim 3; Explore Individual Differences as potential mediators of response to AAI in children with ADHD. Secondary Outcome Exploratory Mediator Analysis; In the proposed study, we will explore how children's individual (a) acute physiological responses during intervention sessions and their individual (b) social interaction quality during intervention sessions may play a role in each of the Main Outcomes. Specifically, we will a) ascertain acute HPA activity (as measured by Cort, and sUA) and acute ANS activity (as measured by HRV and sAA) during intervention sessions across

both treatment conditions and we will b) ascertain the quality of in-session social relationships (child-child) across both treatment conditions as well as the quality of in-session child animal interaction (child-dog) during the AAI sessions (observed child/child & child/dog interaction) at three (3) time points across the 10-week study intervention period (weeks 1, 5, & 10). The acute response and interaction quality measures from each of the three sessions will then be correlated with the degree of change in the primary main outcomes. (e.g., pre-post change in ADHD symptoms, social skills, regulation) and the exploratory main outcomes (e.g., pre-post change in diurnal HPA activity and ANS activity) to examine the potential mediation of individual differences on response to AAI with therapy dogs for children with ADHD. Here we provide an example of one mediation analysis for treatment group (AAI vs Control) as the primary predictor, salivary cortisol response slope at session 5 the potential mediator, and behavioral change (pre-post change) the outcome: First, cortisol response slope² means will be compared between the groups (the mediator must be related to the predictor). If significant, then the relationship between cortisol response slope², and behavioral change will be evaluated for a significant correlation/slope (the mediator must be related to the outcome). Finally a model will be run with both treatment group and cortisol response slope² predicting behavioral change. If the relationship between treatment group and behavioral change is reduced compared to the primary analysis (i.e., with treatment group alone), saliva cortisol response² is interpreted as providing a mediated effect. To obtain estimates of the size and significance of the indirect effects, bootstrapping procedures as described by Shrout and Bolger (2002) will be implemented. Due to the fact that bootstrapping procedures are still limited in the case of multilevel models, an approximation of the Sobel test will also be performed, along with Monte Carlo estimation of confidence intervals but because this aim is exploratory and this is not a fully powered study, results presented will include descriptive and confidence intervals.

Describe the statistical method(s) that will be used to analyze the primary outcome(s) or endpoints:

see previous section

If appropriate describe secondary or post hoc analyses of primary outcome(s) or other exploratory analysis and if necessary, provide a breakdown of the methods used per outcome or endpoint:

Statistical Method to Inform Randomization Bias: Intent to treat bias. To establish equivalence of randomly assigned groups pre-intervention, t-tests will be performed on outcome measures comparing the groups. Means and standard deviations will be obtained and effect sizes calculated. Demographic profiles will be obtained and bivariate significant tests performed to assess the balance expected with randomization. Cohort effects on outcome as well as participation rates will be evaluated to assess any bias related to location, calendar time, or other session characteristics. Participation rates across the intervention will be tracked and compared between the randomized groups. In the spirit of the intent to treat principle (White, Carpenter, and Horton 2012) every effort will be made to conduct follow-up assessments on all randomized participants. Withdrawals will be documented with reason provided. In addition, multi-level modeling allows all cases to remain in a repeated measures model and will be done as a sensitivity analyses to primary analyses done on individuals with at least one follow-up point.

Sample Size Determination: Explain how the overall target sample size was determined (e.g., power analysis; precision estimation), providing justification of the effect size for the primary outcome based on preliminary data, current knowledge/literature and/or cost consideration; if appropriate, provide sample size justification for secondary outcomes. Power analysis should (at least) match the primary outcome/endpoint:

Sample Size. This exploratory study will employ a parallel-group randomized clinical trial design in which 48 participants will be randomly allocated to one of two (2) treatment/intervention groups (AAI and Control) delivered across four (4) cohorts in two (2) waves over the span of two (2) years ($n = 12$ per parallel ten-week cohort) in efforts to inform the specific aims of the study.

Power & Expected Effect Size. Sample size analysis was conducted for randomized controlled design, using SAS PROC power. For the primary analysis of the main outcome domain (Aim 1: ADHD Behavior) with type I error rate of .05 was implemented for a repeated measures analysis evaluating group main effect, treatment main effect, as well as the group*treatment interaction. Effect size estimates from the authors' previous parallel-group randomized study of HAI demonstrated large AAI vs control effect size for problem behaviors (.86) and moderate effects on inattention (.45) ([name] et al., 2018a). For Aim 1, with a projected analysis of $n=48$, this exploratory study will exceed 90% power to detect effect sizes of .19 and above. At a level of 80% power, the minimum detectable effect was determined to be .21. For Aim 2, $n = 48$ will, for each of the two primary physiological outcome domains (Aim 2: Diurnal Pattern Hypothalamic Pituitary Adrenal axis activity; HPA and Autonomic Nervous System activity; ANS), a multilevel model will be constructed to assess pre-post intervention change, post-follow up change, group differences at each assessment, and group differences in degree of change. Models will account for within-subject correlation and within-cohort correlation. Four (4) cohorts of 13 participants each will be recruited for a total enrolled target sample size of 52 families over Years 1 and 2, accounting for an anticipated attrition rate of about 8% which is based on our recently completed study of AAI with ADHD ([name], et al., 2018a) in efforts to yield a total sample of 48.

Research Procedures

Provide a detailed chronological description of the clinical or treatment plan:

See Study Design

List all procedures involving the use and/or collection of photographs, or audio/video recording:
Facial image will be in video or photo Participants' first names may be collected or recorded in either video or audio recording

Specify the total duration of a subject's participation in the study and clearly outline the duration of participation for each study visit and sub-study, as applicable:

See Study Design

List data collection tools (e.g., measures, questionnaires, observational tool) below by clicking the 'Add Line' button. Include additional rows for study instruments, as needed:

The 'Columns' button allows you to display or hide columns in the Study Instrument List.

Name of Tool:

The Child's Sleep Habits Questionnaire (Owens, Spirito, & McGuinn 2000)

Is the data collection tool standardized or validated?

Yes

Please provide data collection tool citation:

Owens, J. A., Spirito, A., & McGuinn, M. (2000). The Children's Sleep Habits Questionnaire (CSHQ): psychometric properties of a survey instrument for school-aged children. *Sleep-New York*, 23(8), 1043-1052.

Will this study require clinical items/ services from UC Irvine Health?

No

Does the research involve the use of **identifiable private information**?

No

Sharing Results with Subjects

Will Individual results be shared with subjects?

No

Will overall study results will be shared with subjects?

The overall study results will be listed on Clinicaltrials.gov

Medical Devices

Risk Assessment

Risks and Discomforts

1. Describe and assess any reasonably foreseeable risks and discomforts associated with each procedure for each subject population – physical, psychological, social, legal or other:
2. If this study will involve the collection of identifiable private information, even temporarily, for which the disclosure of the data outside of the research could reasonably place the subjects at risk, include the risk of a potential breach of confidentiality:

The greatest potential risk for children interacting with dogs include the danger of an animal bite or that a dog might carry diseases with potential transmission to humans.

Also, should there be a breach in confidentiality of data, there is a slight risk that private health information could be shared with individuals who are not members of the study team.

This study involves the collection of participant identifiable data (even if temporary such as for recruitment or compensation purposes), and as such, a breach of confidentiality is a risk associated with the research.

Discuss what steps have been taken and/or will be taken to prevent and minimize any risks/potential discomforts to subjects:

Though these are potential dangers, risks of interacting with participating therapy dogs are minimized by a strict safety screening protocol including a review of animal health, history, certification by reputable therapy animal certification organizations, and dog/handler interview. This safety protocol was developed in a prior study by the Lead Investigator which included eighty-one children and over a dozen therapy animals over the course of 4 years and resulted in zero incidents of injury or disease transmission ([name], Emmerson, Abdullah, Stehli, Fine, & Lakes, 2018) and has since been used in clinical treatment in a wide variety of settings across the nation for over 10 years now. The FirstBeat Bodyguard 2 device is small, unobtrusive and does not require an uncomfortable halter band as they easily affix with two small hypo-allergenic adhesive electrodes designed to remain comfortable and has been found to remain in place during moderate to heavy physical activity, and is safe and acceptable in children ages 7-9 [Martinez, et al, 2016]. Additionally, this device has been found safe and feasibly deployed in studies in both typically developing children and specials population as young as 4 years of age [Jerger et al., 2018, Riquelme, et al, 2018]. There is a minimal risk of discomfort from removing the adhesive discs, similar to removing an adhesive bandage. Wiping the skin with a clean cloth or alcohol prep pad will minimize the risk of irritation. All paper and digital records and saliva samples are de-identified using a coding system in which there is only one linking document for record keeping, recruitment and compensation purposed. Only the LR and the study coordinator have access to this document. All identifying information and digital images and recordings are destroyed immediately after analysis unless participants have given explicit consent to use those images or names for explicit media purposes as designated in the Release Form. Only de-identified data will be shared with non-UCI collaborating researchers.

Certificate of Confidentiality

Is the research partially or wholly funded by NIH (including [NIH Institutes and Centers](#)), or does the research involve identifiable sensitive information that require CoC protections?

Yes

Indicate whether the research is protected by a NIH [Certificate of Confidentiality](#) (CoC):
This research is partially or wholly funded by NIH, including NIH Institutes and Centers. A CoC is automatically issued

Indicate in what situations identifiable private information protected by a CoC will be disclosed ([check all that apply](#)):

As required by Federal, State, or local laws, excluding instances of disclosure in any Federal, State, or local civil, criminal, administrative, legislative, or other proceeding. Some examples are laws that require reporting of child or elder abuse, some communicable diseases, and threats to harm yourself or others

Potential Benefits

Is there the prospect of a direct benefit anticipated for subjects?

Yes

Describe the potential benefits subjects may expect to receive from participation in this study:
Participants and their parents may experience improved social skills including improved self-esteem and pro-social behavior and reduced symptoms of inattention and oppositional behavior.

Specify the expected potential societal/scientific benefit(s) of this study:

The possible benefits to science and society include providing information about how potential biological responses to animals may enhance treatments for children with ADHD. This information is important as there are few evidence-based non-pharmacological interventions for this group of individuals who remain at risk for poor life outcomes despite the effectiveness of medicines for the symptoms of ADHD.

Alternatives to Participation

Describe the alternatives to participation in the study available to prospective subjects. Include routine (standard of care) options as well as other experimental options, as applicable ([check all that apply](#)):

Routine standard of care available

Specify the routine standard of care:

The known alternative procedures for decreasing the symptoms of ADHD include treatment with medicines that have been found to decrease symptoms (e.g., Dexedrine®, CONCERTA®, Focalin®, Adderall®, Adderall® XR, Ritalin®, Ritalin LA®, etc.). The known alternative procedures for improving social skills for children with ADHD include behavioral parent training. These alternatives will not be administered during the course of this study.

Participant Compensation

Will subjects be compensated?

Yes

Specify whether compensation is applicable and, if so, the method, amount and schedule of compensation (**Check all that apply**):

Cash

Cash Compensation

Specify cash amount:

\$60.00

Cash schedule:

Other

Specify 'Other' cash schedule:

After each Laboratory School Day
(3)

Will the cash compensation method include all subjects?

Yes

Will subjects be reimbursed for out-of-pocket expenses?

No

Confidentiality of Research Data

Information and/or Biospecimens Storage

Indicate how information and/or biospecimens (including signed consent forms) will be stored
(check all that apply):

Biospecimens will be stored in a locked lab/refrigerator/freezer that is not accessible to non-study team members

Information will be maintained electronically. Information will be password protected and maintained in an encrypted format

Information will be maintained in hard copy. Information will be stored in a locked area that is not accessible to non-study team members

Biospecimens Storage

Specify where the biospecimens will be stored in a locked lab/refrigerator/freezer:

Biospecimens will be stored in a locked lab freezer at the contracted lab, Salimetrics, Inc.

Encrypted Format

Specify where the information will be maintained electronically:

All electronic information is maintained in Redcap

Hard Copy

Specify where the information will be maintained in hard copy:

Hard copy data will be stored in a locked cabinet in the private office of the LR and not accessible to non-study team members.

Will subject/patient identifiers be collected or retained?

Yes

Subject/Patient Identifiers

Will any subject/patient identifiers be collected or retained for data analysis, recruitment, consenting and/or compensation (**check all that apply**)?

All elements of dates (except year) for dates that are directly related to an individual: birth date, admission date, discharge date, death date, and all ages over 89

All geographic subdivisions smaller than a state: street address, city, county, precinct, ZIP code, and geocodes

Any other unique identifying number, characteristic, or code

Email addresses

Full-face photographs and any comparable images

Names

Telephone numbers

Specify any other unique identifying number, characteristic or code:

audio-video recordings

Will a code be used to link subject/patient identifiers with the information and/or biospecimens?

A code will be used. Subject/Patient identifiers will be kept separately from the information and/or biospecimens. The code key will be destroyed at the earliest opportunity, consistent with the conduct of this research

Will research data/biospecimens be transported or maintained on portable devices (e.g., laptop, smartphone, external hard drive, etc.)?

Yes

Specify the device(s) or method(s) of transportation:

portable devices

Explain why transporting or maintaining subject/patient identifiable data/biospecimens on portable devices is necessary:

Audio and video recordings will be recorded on portable devices, which will be placed in a locked cabinet following evening sessions and then immediately downloaded to a secure server within 24 hours of recording and deleted from the portable device.

Specify who will have access to subject/patient identifiable information/biospecimens as part of this protocol (**check all that apply**):

Authorized UCI personnel (such as the research team) and appropriate institutional officials: such as the Office of Human Research Protections (OHRP) Regulatory entities such as the Food and Drug Administration (FDA), the National Institutes of Health (NIH)

Specify whether subject/patient identifiers be disclosed in presentations and/or publications:
Subject/Patient identifiers will not be disclosed

Specify how long all subject/patient identifiers will be retained. This includes identifiers stored in paper format, stored electronically as well as video recordings, audio recordings, photographs, etc.:

Destroyed after publication/presentation or end of protocol

Will any identifiable photos or audio/video recordings be collected or used?

Yes

Collection of Photographs, or Audio/Video Retention & Recording

Will identifiable audio recordings be collected?

Yes

How will the audio recordings be transcribed?

Identifiable audio recordings
transcribed by the study team

Specify timeframe for the audio transcription:
within 2 years of the study
completion

Will the identifiable audio recordings be de-identified?

No

Provide rationale on why identifiable audio recordings will not be de-identified:

First names may be called during the audio recording of intervention group sessions. No identifiable information will be used in the labeling of audio recordings

Will identifiable video recordings be collected?

Yes

How will the video recordings be transcribed?

Identifiable video recordings
transcribed by the study team

Specify timeframe for the video transcription:

within 2 years of the study
completion

Will the identifiable video recordings be de-identified?

No

Provide rationale on why identifiable video recordings will not be de-identified:

Provided parents or LAR provide explicit permissions, photographs and/or audio/video recordings may be used as specifically specified (i.e., training, presentation). See Release Form

Will identifiable photographs be collected?

Yes

Will the identifiable photographs be de-identified?

No

Provide rationale on why identifiable photographs will not be de-identified:

Provided parents or LAR provide explicit permissions, photographs and/or audio/video recordings may be used as specifically specified (i.e., training, presentation). See Release Form

Research Information and/or Biospecimens Retention

Indicate how long research information/biospecimens will be retained:

In accordance with UCOP policy, information/biospecimens will be retained for 10 years after the end of the calendar year in which the research is completed, unless otherwise specified in the award agreement

Will research information and/or biospecimens be shared?

No

Attachments

If required documentation is not provided, the submission is incomplete and your Application will be returned to you. Be sure to upload each document as required. If changes are needed, go back to

the sub-section to revise your selections.

Maximum file size is 30MB

All UCI templates are available on the Human Research Protections [Applications & Forms page](#) or Human Stem Cell Research [Applications & Forms page](#).

To access approval documents where UCI will rely on another IRB, including commercial IRBs, visit their respective online portals. Frequently used commercial IRB portals include:

- WIRB Copernicus Group's [WCG IRB Connexus](#)
- Advarra's [CIRBI](#)
- SMART [Online Reliance System \(ORS\)](#)

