Describe the purpose, specific aims or objectives and specify the hypotheses or research questions to be studied:

The purpose of this research is to address gaps in understanding of the mechanisms of AAI and how these mechanisms may differ across special populations hinder progress in the application of AAI, and limit the acceptability and availability of this integrative health care practice. Our bio-social mechanistic hypothesis contends that dogs elicit physiological responses related to arousal of EF systems, thereby enhancing response to treatments. Furthermore, candidate individual differences potentially mediate outcomes. This work will explore these hypotheses; 1) we suspect AAI will result in enhanced social-behavioral outcomes and improved diurnal patterns of HPA and ANS activity for these children and 2) we suspect acute physiological responses to AAI (markers of HPA & ANS) and social interaction quality (child/child and child/dog) will mediate main outcomes.

Specific Aims Specific Aim 1: To replicate previous findings that social-behavioral outcomes are improved for children with ADHD when they participate in an 8- 10 week manualized AAI with therapy dogs. Specific Aim 2: To explore if diurnal patterns of physiological markers of Hypothalamic Pituitary Adrenal axis (HPA) activity (salivary cortisol; Cort and uric acid; sUA) and Autonomic Nervous System (ANS) activity (heart-rate variability; HRV, and salivary alpha-amylase; sAA) are improved over time for children with ADHD in response to an 8- 10 week manualized AAI with therapy dogs. Specific Aim 3: To explore if potential individual differences in children with ADHD are manifested during intervention sessions and if these differences mediate primary and exploratory main outcomes from an 8- 10 week manualized AAI with therapy dogs. Specific individual differences explored include; acute physiological responses during intervention sessions as measured by markers of HPA & ANS activation (Cort, sUA, sAA, & HRV) and the quality of social interaction (child/child and child/animal) during sessions.

Provide the scientific or scholarly rationale for the research and describe the relevant background information and the specific gaps in current knowledge that this study intends to address:

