The proposed research will run a Parallel-Group Randomized Controlled Trial, employing an exploratory parallel-group randomized controlled trial study design and utilizing a multi-method and multi-source assessment protocol. a. The study is currently planned to take place at The Children's School at [name] b. We will use a repeated-measure within-subject design, gathering measurement of main outcomes at three time points to assess the efficacy of AAI for children with ADHD who are participating in a short-term intervention with or without the assistance of therapy dogs. A linear, repeated measures design will be utilized for our primary, and exploratory main outcome. c. Over the course of about 4 months, children will participate in treatment and assessment for a total up to approximately 16-20 hours) and parents will participate in approximately 6-9 hours of assessment. d. Children and their parents will first attend a screening visit that will last 2-3 hours to determine eligibility. e. If eligible, participation will require participants to attend group sessions for integrative, non-medical treatments for ADHD, once weekly (one weekday after school to be determined as space permits for about 2 hours per session (for a total of about 16-20 hours). These play group sessions may or may not include the participation of up to 3-4 certified therapy dog/handler dyads. These group sessions will be video recorded to capture child-child, child-dog, and dog behavior. f. Participation will also require child participants to attend three (3) Saturday "Laboratory School" assessment visits, immediately prior to and after the intervention period and then five weeks later. Each of these assessments will last approximately five to six (5-6) hours (about 18 total hours over three visits) for child participants and up to 2 hours each of three visits for parents (about 6 hours total). "Laboratory School" recess sessions will be video taped to capture observed child-child interactions. g. Participants will also be requested to wear a device used to collect heart rate (FirstBeat monitor) during the assessment days (3) and intervention sessions (3) and on the night prior to participation in the three (3) Saturday "Laboratory School" assessment visits. The FirstBeat monitors which have been found to be acceptable, feasible, safe and reliable for collection in several youth samples. For heartrate collection, parents will be instructed on how to affix a

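### Do the differing follow-up intervals (five versus six weeks) and course lengths (8-10 versus 10 weeks) undermine the planned analysis?

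*Combined protocol and SAP*

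**What the plan says.** All references are to the combined protocol and SAP.

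**Follow-up.** Study Design, item (f), sets the three Saturday assessment visits "immediately prior to and after the intervention period and then five weeks later". Under Statistical Considerations, Specific Aim 2 lists the three diurnal profiles as baseline, "end of treatment patterns, and then patterns at 6 weeks post-treatment". The other mention of six weeks in that section describes the investigators' previous study, not this trial.

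**Course length.** Each of the three specific aims refers to an "8- 10 week manualized AAI with therapy dogs". Study Design, item (e), has sessions "once weekly (one weekday after school to be determined as space permits for about 2 hours per session", for a total of about 16-20 hours. The statistical text is narrower. Aim 2 speaks of "measurable changes in physiological responses to a short-term AAI (10 weeks" in brackets, and the sample size text counts children "per parallel ten-week cohort".

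**Mediator sessions.** Aim 3 takes its in-session measures "at three (3) time points across the 10-week study intervention period (weeks 1, 5, & 10" and continues: "The acute response and interaction quality measures from each of the three sessions will then be correlated with the degree of change" in the main outcomes. Its worked example uses the cortisol slope at session 5. Study Design, item (g), mentions three monitored sessions without giving their week numbers.

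**The concern.** Read side by side, the procedures and the analysis plan seem to describe two different trials: one with follow-up at five weeks and a course that may end in week 8, the other with follow-up at six weeks and a course that always reaches week 10.

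Two things could be at stake. A durability result might be reported under an interval that was not the one delivered. And in a cohort of 8 or 9 weeks the third mediator session would not exist. The analysts would then have to choose, with the data in hand, whether to substitute another session or treat the point as missing. The visible text gives neither a common anchor for follow-up nor a replacement rule for week 10.

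**Working it through.** **1. The plan's own session hours.** Inputs: one session a week of about 2 hours, total about 16-20 hours (Study Design, item e).

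- 8 × 2 = 16 h; 9 × 2 = 18 h; 10 × 2 = 20 h.

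The stated total is reproduced by 8 to 10 sessions. It does not prove that a short course is planned, because 10 × 1.6 = 16 h fits too. The total duration of about 4 months does not settle it either. Adding course, follow-up and the 21-day pre-treatment window gives 8 + 5 + 3 = 16 weeks to 10 + 6 + 3 = 19 weeks. At 4.345 weeks per month that is 3.7 to 4.4 months.

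**2. Follow-up interval.** Inputs: sessions on a weekday (item e), visits on a Saturday, third visit five weeks (35 days) after the second (item f). Formula: days from last session to follow-up = days from last session to post-visit + 35. Six weeks is 42 days.

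| Post-visit | Days from last session (Mon to Fri) to post-visit | Days to follow-up | Weeks | Minus 42 |
|---|---|---|---|---|
| Saturday of the same week | 5, 4, 3, 2, 1 | 40, 39, 38, 37, 36 | 5.7 to 5.1 | -2 to -6 |
| Following Saturday (assumption) | 12, 11, 10, 9, 8 | 47, 46, 45, 44, 43 | 6.7 to 6.1 | +5 to +1 |

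If six weeks were also counted from the post-visit, which is not its plain meaning, the gap would be 42 − 35 = 7 days.

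**3. What the model uses.** The Power & Expected Effect Size section describes the Aim 2 multilevel model as estimating change from pre to post, change from post to follow-up, and group differences at each assessment. Time enters as visit, not as days. Moving the third visit by a few days changes no term in the model.

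**4. Course length against the mediator weeks.**

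- 8 weeks: sessions 1 and 5 exist, session 10 does not.
- 9 weeks: the same.
- 10 weeks: all three exist.

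Ten weeks lies inside the range in the aims and matches Aim 2, Aim 3 and the sample size text. The background under Aim 1 also gives a reason for 10, drawn from the previous study. A 10-week course therefore satisfies every statement.

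**5. Size if one cohort did run short (hypothetical).** With 12 of the 48 children in a cohort and three sessions each, 12 × 1 = 12 of 48 × 3 = 144 child-session values would be missing for a measure taken in both arms, or 8.3%. The session-10 correlation would rest on 48 − 12 = 36 children. Sessions 1 and 5, including the worked example, would be complete. The main outcomes would still be assessed three times, because those visits are tied to the start and end of the intervention and not to a week number.

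**The case for a change.** The best case for acting is that both mismatches are in current text, nothing had been analysed at the time of the renewal, and alignment costs only wording and one recorded date per child. The form asks that the analysis match the aims, and on course length it does so only in part. When asked for precise endpoint definitions, the form only points back to the text above. A substitution rule is better settled before the data are seen than after.

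Much of that is fair. The anchor is unstated in the text available, and a reader cannot tell exactly which follow-up interval was meant. No replacement for week 10 is given either. These absences are firm only for the visible text: Figure 1, cited beside the description of the three time points, and the separately attached Protocol Narrative could not be seen.

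What does not stand is the step from loose wording to a defect in the analysis. Five weeks from one event and six weeks from an earlier one can both be roughly true. The six-week figure is attached only to Aim 2, an exploratory outcome; no conflicting interval is given for the primary behavioural outcome. The missing rule matters only in a case the documents permit but do not predict. It would then affect one of three points in an aim the plan itself calls exploratory and not fully powered, reported with descriptive results and confidence intervals.

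**Conclusion.** No change to the plan follows. The trial can be run as written, and the model, sample size (48 analysed, 52 enrolled), power and comparison of AAI with control are the same under either reading of the follow-up interval. The mismatch amounts to 1 to 6 days between two labels for one visit, at most 7, and to one undefined exploratory mediator point if a cohort ends before week 10. Analysts would ordinarily fill both gaps by reporting the actual days from last session to follow-up and the delivered course length by cohort.

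This rests on three assumptions: sessions fall Monday to Friday, the post-visit is on the first or second Saturday after the last session, and cohorts run the 10 weeks that the statistical text specifies. If several cohorts ran short, the third mediator point would carry less information, but the main outcomes would keep their three assessments.

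The statements on follow-up interval and on course length still have to be reconciled as a matter of wording. That choice belongs to the investigators, and nothing here says which schedule is right.
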